6.4 Adverse Event Severity

The severity of each AE will be assessed at the onset by a physician. When recording the outcome of the AE the maximum severity of the AE experienced will also be recorded. The severity of each AE will be graded according to the Common Terminology Criteria for Adverse Events (CTCAE) version 5.0:

- Grade 1:** Mild; asymptomatic or mild symptoms; clinical or diagnostic observations only; intervention not indicated.
- Grade 2:** Moderate; minimal, local or non-invasive intervention indicated; limiting age-appropriate instrumental activities of daily living.
- Grade 3:** Severe or medically significant but not immediately life-threatening; hospitalization or prolongation of hospitalization indicated; disabling, limiting self-care activities of daily living (i.e., preparing meals, shopping for groceries or clothes, using the telephone, managing money).
- Grade 4:** Life-threatening consequences, urgent intervention indicated.
- Grade 5:** Death related to AE

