4.4 Patient Withdrawal and Replacement

If a patient is pregnant, the patient will be withdrawn from study treatment immediately.

A patient may be withdrawn for any treatment related adverse event or clinically significant findings in clinical labs or other vital signs that are deemed by the investigator to pose an unacceptable risk to the patient. If the study is interrupted due to any of the criteria listed above, the patient may undergo unscheduled assessments to evaluate his/her status. Additional subsequent visits may be required to assess event outcomes.

Study treatment may be discontinued, interrupted or dose reduced for any grade 3 adverse event that is possibly or probably related to study treatment. Study treatment will be discontinued for any grade 4 adverse event that is possibly or probably related to study treatment

Patients may also be discontinued from the study at any time for any of the following reasons:

- Adverse event
- Death
- Lost to follow-up
- Investigator decision
- Pregnancy
- Protocol deviation
- Study terminated by Sponsor
- Withdrawal by subject

A patient may be withdrawn from the study at any time due to the following adverse events based on the known safety profile and mechanism of the drug:

- Dehydration requiring hospitalization
- A laboratory result of total cholesterol and triglycerides $> 2 \times$ ULN
- Allergic reaction requiring hospitalization

A patient may be withdrawn from the study at any time due to the following adverse events:

- A laboratory result of ALT or AST $> 3 \times$ ULN, total direct bilirubin $> 2 \times$ ULN or serum creatine > 2.5 ULN
- Abnormal cardiac findings such as a clinically significant abnormal heart rate or rhythm, left bundle branch block with QRS interval > 110 msec or first-degree AV block with PR interval > 220 msec.

A patient may be withdrawn by the investigator or the sponsor if enrollment in the study is deemed inappropriate, the study plan is violated, or for administrative and/or safety reasons.

A patient may elect to discontinue study participation at any time for any reason without prejudice to his/her

future medical care by the physician or at the institution. The investigator will document the specific reason why consent was withdrawn.

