7.2 Statistical Analysis

Effects of treatment will be compared using Intent-to-Treat principles using ANCOVA with BMI, gender and baseline fasting C4 as covariates. In order to reach 30 subjects, accrual will be set at 36 to replace any volunteer(s) who withdraw prior to taking less than 1 day of dosing. Any Subject who receives more than 1

day of dosing will be consider completed using the Intent-to-Treat analysis.

Primary endpoints are change in fasting serum C4 levels from baseline to Day 28 and change in stool consistency based on Bristol Stool Form Scale, BSFS from baseline to Day 28.

Secondary endpoints are

- Absolute change in stool consistency from baseline to Day 14 and Day 28 of treatment
- Average daily stool consistency score at Day 14 and Day 28 of treatment
- Maximum abdominal pain score rated by patient using an 11-point scale, 0 to 10 inclusive with 0 as none and 10 as worst imaginable pain
- Absolute change in abdominal pain from baseline to Day 14 and Day 28 of treatment
- Number of bowel movements per week
- Change in total fecal bile acid concentration between baseline and Day 28
- Proportion of fecal secretory (CDCA+ DCA) bile acid as measured in a single, random stool sample by a validated laboratory assay.
- Proportion of fecal primary (CDCA + CA) bile acid as measured in a single, random stool sample by a validated laboratory assay.
- Total fecal bile acid concentration in a single, random stool sample as measured by a validated laboratory assay.
- Total aldafermin concentration in serum as measured by a validated laboratory assay

Adverse events (AEs) will be listed and summarized by system organ class and preferred term, as well as according to severity and causality/relationship to study treatment.

Observed values for clinical laboratory tests, vital signs and safety 12-lead ECGs will be summarized by treatment. Observed values will be classified as normal, abnormality that is not clinically significant, and clinically significant abnormality by treatment.

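### The Grade 3 severity line in section 6.4 defines self-care by tasks that in plain meaning belong to Grade 2, so the two grades overlap and a moderate event can be recorded as severe

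*Combined protocol and SAP*

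**What the plan says.** Section 6.4 names an external scale: "The severity of each AE will be graded according to the Common Terminology Criteria for Adverse Events (CTCAE) version 5.0". After a colon it prints its own text for each grade.

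- Grade 2 (moderate) has the functional criterion "limiting age-appropriate instrumental activities of daily living", with no examples.
- Grade 3 (severe) has the functional criterion "disabling, limiting self-care activities of daily living (i.e., preparing meals, shopping for groceries or clothes, using the telephone, managing money".

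The grade is used in two places. Section 7.2 summarizes adverse events by system organ class and preferred term, "as well as according to severity and causality/relationship to study treatment". Section 4.4 links the grade to treatment action. At Grade 3, "Study treatment may be discontinued, interrupted or dose reduced for any grade 3 adverse event" when the event is possibly or probably related. At Grade 4, "Study treatment will be discontinued for any grade 4 adverse event that is possibly or probably related to study treatment".

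**The concern.** Cooking, shopping, telephone use and handling money are household and community tasks. In ordinary usage they are not care of one's own body. Because the list is introduced by i.e. and not e.g., it reads as the definition of the Grade 3 limit. The only list of activities a grader sees is thus attached to the higher grade, while the Grade 2 category it describes has none. Nothing in section 6.4 says which line prevails when an event fits both.

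Two things are at stake. The by-severity tables may count some moderate events as severe, and graders who follow the printed line may differ from graders who follow the named scale. In addition, section 4.4 attaches a grade-based treatment provision to Grade 3 and none to Grade 2, so the boundary between these grades decides whether that provision applies.

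**Working it through.** The plan states no figure on this point, so the check compares texts. One line of arithmetic gives scale.

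**1. Inputs.** The Grade 2 and Grade 3 lines and the named scale come from section 6.4. The treatment-action provisions come from section 4.4, the study-level stopping rule from section 4.5, the use of severity from section 7.2, and the 15 patients per group from section 2.1 and the synopsis.

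**2. The two lines side by side.**

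| | Grade 2 | Grade 3 |
|---|---|---|
| Activity limited | Instrumental | Self-care |
| Activities listed | None | Meals, shopping, telephone, money |
| Plain meaning of the list | – | Instrumental |

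**3. A test case.** Take an event whose only functional effect is that the patient cannot shop. It limits an instrumental activity, so the Grade 2 criterion is met. Shopping is on the Grade 3 list, so the literal Grade 3 functional criterion is met too. The lines overlap for every task on the list.

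**4. Where the grade goes next.**

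- Section 7.2: the event enters the severity summary at whichever grade was recorded.
- Section 4.4: if recorded as Grade 3 and judged possibly or probably related, it falls under the permissive provision. If recorded as Grade 2, no grade-based provision applies.
- Section 4.5: the study-level rule counts hospitalization for dehydration or allergic reaction and does not use the grade. The overlap does not touch it.

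**5. Scale.** Let k be the number of patients in an arm whose only Grade 3 event is there because of the overlap. The arm's severe-event proportion rises by k/15. For k = 1 this is 1/15 = 6.7 percentage points, and for k = 0 it is nothing. The documents give neither an event rate nor a misgrading probability, so k cannot be estimated. The 6.7 points are the weight of one patient, not a predicted bias.

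**The case against.** The strongest reply is that this is a wording slip with little reach. Section 6.4 names CTCAE version 5.0, so a physician who grades from that scale need not misgrade. The Grade 3 line also contains more than the list: it speaks of severe, medically significant and disabling events and of hospitalization. Severity is only summarized, with no test planned. Under section 5.5 the staff who evaluate safety do not know the assignments, so the same wording applies to both arms. Section 4.4 already lets the investigator withdraw a patient for a treatment-related event at any grade.

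Much of this stands and limits the point, but it does not remove the overlap. The section prints its own grade text, and a grader working from the protocol will use it. If some follow the print and others the named scale, grading becomes inconsistent. Blinding does not correct an inflated count.

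A reader might infer several stronger things that the documents do not support:

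- *That moderate events will be graded severe.* They can be. The named scale and the rest of the Grade 3 line leave room for correct grading.
- *That section 6.4 resolves the overlap upward.* It says that "the maximum severity of the AE experienced will also be recorded", but this comes in addition to severity at onset and most naturally means the peak over the event's course. It is not a rule for choosing between two definitions.
- *That Grade 3 triggers a stopping rule.* The provision is permissive, offers interruption or dose reduction as alternatives, and covers only possibly or probably related events. Mandatory discontinuation stands at Grade 4.
- *That Day 28 values would be lost.* The documents do not say that a change in treatment cancels the Day 28 measurement, and section 7.2 keeps anyone with more than 1 day of dosing in the Intent-to-Treat analysis.
- *That bowel symptoms in this population typically limit shopping.* The diary and the quality-of-life form ask about urgency, long trips and nearness to a toilet, but the documents give no frequency. Under section 6.2 a pre-existing condition is given as an adverse event when it worsens, becomes more frequent or shows new signs, so limitation already present at baseline is not shown to be one.

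**Conclusion.** The point holds as a drafting inconsistency in an operative definition. The printed Grade 2 and Grade 3 lines overlap for the listed tasks, and an event limiting only those tasks can be recorded at the higher grade. The consequences are possible inflation of the severe-event summaries and possible entry of related events into a discretionary provision.

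The conclusion rests on two assumptions: that the listed tasks are instrumental in their plain meaning, since the documents do not themselves list instrumental activities, and that at least some graders work from the printed text. Confidence in the overlap is high. The number of events affected is unknown and could be zero.

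**What to change.** Reconcile the Grade 2 and Grade 3 lines of section 6.4 with each other and with the scale the section names. Attach the list of tasks to the instrumental-activities wording in Grade 2 and remove it from Grade 3. If Grade 3 is to carry examples, check them against CTCAE version 5.0 before printing them. Make the same change in any grading instructions. Before database lock and under the blind, recheck any events already graded on limits of this kind.

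Realigning the lines affects which events reach the Grade 3 provision in section 4.4, so the two sections should be read together when the amendment is made. No view is taken on what that provision should say.

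The cost is a short amendment, submitted to the IRB as section 8.2 requires, and a brief review of graded events. It needs no new data, no change in sample size and no change to the efficacy analysis.

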6.5 Adverse Event Relationship

The investigator is obligated to assess the causal relationship between the study treatment and each occurrence of an AE. The AE causal relationship to study treatment must be characterized as one of the following categories:

Not Related:	The AE does not follow a reasonable temporal sequence from administration of the study treatment, does not abate upon discontinuation of the study treatment, does not follow a known or hypothesized cause-effect relationship, and (if applicable) does not reappear when the study treatment is reintroduced, furthermore, there may exist a clear alternative medical explanation (e.g., underlying disease state) or association with study procedure or conduct.
Unlikely Related:	The temporal association between the AE and the study treatment is such that the study treatment is not likely to have any reasonable association with the AE.
Possibly Related:	The AE follows a reasonable temporal sequence from administration of the study treatment and follows a known or expected response to the study treatment but could have also been produced by a number of other factors.
Probably Related:	The AE follows a reasonable temporal sequence from administration of the study treatment and cannot be reasonably explained by the known characteristics of the patient's clinical state, environmental, or toxic factors, or other modes of therapy administered to the patient.
Related:	The AE follows a reasonable temporal sequence from administration of the study treatment, abates upon discontinuation of the study treatment, follows a known or hypothesized cause-effect relationship, and (if appropriate) reappears when the study treatment is reintroduced.

The Principal Investigator will use clinical judgment to determine the causal relationship. Alternative causes, such as underlying disease(s), concomitant therapy, and other risk factors, as well as the temporal relationship of the event to the study treatment administration should be considered and investigated. The Principal Investigator should consult the IB and the Product Information of marketed products within the study treatment class, when applicable. For each AE, the Principal Investigator must document in the medical notes that he/she has reviewed the AE and has provided an assessment of causality. There may be situations in which an SAE has occurred, and the Principal Investigator has minimal information to include in the initial report; however, the Principal Investigator should always make an initial assessment of causality for every event. The Principal Investigator may change his/her opinion of causality based on subsequent receipt of information and send an SAE follow-up report with the updated causality assessment. The causality assessment is one of the criteria used when determining regulatory reporting requirements.

Any SAE that is ongoing when the subject completes the study or discontinues the study will be followed by the Principal Investigator until the event resolves, stabilizes, or returns to baseline status.

6.6 Clinical Laboratory Tests

Clinical safety laboratory tests will be performed at the study site at Visit 1 Screen or Visit 2 and Visit 5 End of Study. These tests include the Comprehensive Metabolic Panel, calcium, creatinine, sodium, potassium,

albumin, alkaline phosphatase, total bilirubin, carbon dioxide, chloride, glucose, total protein, BUN, AST, and ALT. Hematology includes a CBC with differential. A lipid panel including total cholesterol, HDL, LDL and triglycerides will be performed. Analysis of the urine will be completed by a standard urine dipstick method with microscopy. The investigator will the laboratory report, document the review, and record any clinically relevant changes as AEs.

6.7 Electrocardiograms

Single 12-lead ECGs will be recorded with subjects in a supine position at Visit 1 Screen and Visit 5 End of Study. Additional ECGs may be taken at any other times, if deemed necessary by the investigator. All ECG tracings will be reviewed by the Principal Investigator or designee.

6.8 Assessment of Abdominal Pain, Stool Frequency and Consistency

Patients will complete a daily bowel pattern diary throughout the study to record and assess their most severe abdominal pain on an 11-point scale and timing of each bowel movement, consistency based on Bristol stool form scale, ease of passage, and sense of completeness of evacuation. Ease of stool passage was also assessed based on a 7-point scale (1: manual disimpaction; 2: enema needed; 3: straining needed; 4: normal; 5: urgent w/o pain; 6: urgent w/pain; 7: incontinent). The Bristol stool scale and a sample diary page are included in the protocol appendices.

6.9 Assessment of Bile Acid Kinetics

Assessment of BA synthesis and fecal excretion (uniquely available in USA at Mayo Clinic):

Serum 7 α -hydroxy-4-cholest-3-one (7 α -HCO or C4) measures hepatic cholesterol synthesis and is a validated method for BAM/BAD (18,19). Serum C4 (ref. 20, assay based on ref. 21) is positively correlated with fecal BA excretion [$r_s = 0.61$, $p < 0.001$ (4)].

Serum fibroblast growth factor 19 (FGF19), a measure of feedback regulation of BA synthesis (22), will be measured by ELISA (R&D Systems, Minneapolis, MN).

Fecal BA excretion: Using HPLC/tandem mass spectrometry, we adapted a method (23) to measure fecal total and individual BAs in a RANDOM stool sample. We have previously shown that fecal total BA (4), and secretory primary and secondary BAs [chenodeoxycholic (CDCA) and deoxycholic acids (DCA)] are higher in IBS-D, whereas CDCA is decreased and non-secretory lithocholic acid increased in IBS-C (24)]. Total fecal bile acids and primary CDCA will be measured.

6.10 Assessment of Aldafermin Pharmacokinetics

Trough concentrations of aldafermin will be determined by a validated PK laboratory assay performed at a bioanalytical CRO, Frontier Laboratories, using serum samples obtained at baseline, Day 14 and Day 28.

Anonymized serum samples will be provided for pk analysis. The samples will be labelled with a de-identified study number that cannot be linked to the patient's identity without use of a key which will be kept in a password-protected secure server at Mayo accessible only to the study team.

Samples will be stored at Frontier Laboratories only until the pk analysis is performed which must be done in a reasonable amount of time. After performing the pk analysis, Frontier Laboratories will discard the samples.

7. STATISTICAL CONSIDERATIONS

7.1 Sample Size and Statistical Power

Based on the endpoints of interest in patients with bile acid diarrhea [12], the proposed sample sizes have ~80% power (2-sided $\alpha=0.05$) to detect clinically relevant effect sizes in serum C4 and stool form (expressed as detectable difference $[\Delta]$ in 2 groups:

Table 1: Detectable differences based on 80% power in patients with BAD *not* receiving BA sequestrant

Response	Mean (SD)	Detectable Δ absolute with n=9 per group
Serum C4 ng/mL	72.3 (45.6)	64.1 (1.34*SD or 89 % of baseline mean)
% fecal primary BA	15.7 (20)	28.1 (1.79*SD or 179 % of baseline mean)
# BMs per week	15.1 (7.1)	10.0 (1.41*SD or 66 % of baseline mean)
Stool form (BSFS 1-7 scale)	4.4 (1.12)	1.58 (1.41*SD or 35.9 % of baseline mean)

Based on our previous open-label study demonstrating effects of a bile acid sequestrant (colesevelam) as a typical baseline results for patients on bile acid sequestrants:

Table 2: Detectable differences based on 80% power in patients with BAD receiving BA sequestrant

Response	Mean (SD)	Detectable Δ absolute with n=6 per group
Serum C4 ng/mL	112.5 (50.6)	90.8 (1.79*SD or 80.7 % of baseline mean)
% fecal primary BA	2.7 (7.4)	13.3 (1.80*SD or 492% of baseline mean)
# BMs per week	21.7 (7.1)	12.75 (1.80*SD or 58.8 % of baseline mean)
Stool form (BSFS 1-7 scale)	4.6 (0.6)	1.08 (1.80*SD or 23.5% of baseline mean)

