2.2 Study Endpoints

Primary Endpoints

1. Change in fasting serum C4 levels from Baseline to Day 28
2. Change in stool consistency based on the Bristol Stool Form Scale, BSFS from Baseline to Day 28

Secondary Endpoints

1. Stool consistency based on Bristol Stool Form Scale, BSFS
 - a. Absolute change in stool consistency from baseline to Day 14 and Day 28 of treatment.
 - b. Average daily stool consistency score at Day 14 and Day 28 of treatment

[figure not shown]
2. Maximum abdominal pain score rated by patient using an 11-point scale, 0 to 10 inclusive with 0 as none and 10 as worst imaginable abdominal pain.
3. Absolute change in abdominal pain from baseline to Day 14 and Day 28 of treatment.
4. Number of bowel movements per week
5. Change in total fecal bile acid concentration between baseline and Day 28.
6. Proportion of fecal secretory (CDCA + DCA) bile acid as measured in a single, random stool sample by a validated laboratory assay.
7. Proportion of fecal primary (CDCA + CA) bile acid as measured in a single, random stool sample by a validated laboratory assay.
8. Total fecal bile acid concentration in a single, random stool sample as measured by a validated laboratory assay.
9. Total aldafermin concentration in serum as measured by a validated laboratory assay

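### The stool-form rows of the power tables use the SD of a BSFS level, but the primary endpoint is an unadjusted change; with equal SDs, power reaches 80% only if the baseline-to-Day 28 correlation is about 0.5 or higher

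*Combined protocol and SAP*

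**What the plan says.** Section 2.2 defines the second primary endpoint as "Change in stool consistency based on the Bristol Stool Form Scale, BSFS from Baseline to Day 28", and section 7.2 repeats it. Section 7.2 (and the synopsis, under Statistical Methods) plans an "ANCOVA with BMI, gender and baseline fasting C4 as covariates". Baseline BSFS is not among the covariates.

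Section 7.1 claims about 80% power at two-sided alpha 0.05 and supports it with two tables:

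- Table 1 (no sequestrant, 9 per group): stool form has mean 4.4 and SD 1.12, and the detectable difference is "1.58 (1.41*SD or 35.9 % of baseline mean").
- Table 2 (on sequestrant, 6 per group): stool form has mean 4.6 and SD 0.6, and the detectable difference is 1.08, or 1.80 SD. The text introducing this table calls its inputs "typical baseline results for patients on bile acid sequestrants".

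The synopsis repeats the claim of about 80% power for 15 per group, for serum C4 and stool consistency, without stating a detectable difference. Neither an SD of the change nor a baseline-to-Day 28 correlation appears anywhere in the documents.

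**The concern.** The variance of a change score depends on how strongly the two measurements are correlated; the variance of a single level does not. A mean of 4.4 or 4.6 on a 1-7 scale is a level, and both tables express the detectable difference as a percentage of the baseline mean. The tables therefore carry the spread of a level over to an endpoint that is a change.

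For an endpoint adjusted for its own baseline, this substitution is usually harmless. Stool form is not adjusted in that way: the only baseline outcome in the model is C4. The stated 80% therefore belongs to a variance that the planned stool-form analysis does not use. What is at stake is whether 1.58 and 1.08 points describe what the trial can detect on one of its two primary endpoints.

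**Working it through.** **Inputs.** Section 7.1: SD 1.12, difference 1.58, n = 9 per group (Table 1); SD 0.6, difference 1.08, n = 6 per group (Table 2); two-sided alpha 0.05; power about 80%. Section 7.2: the covariates. Assumptions of this check: rho (correlation of baseline with Day 28 BSFS) from 0.2 to 0.7, and equal SDs at the two times.

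**Step 1. Reproduce the plan's figures.** Two-sample t-test, noncentral t with 2n - 2 degrees of freedom and noncentrality difference / (SD × sqrt(2/n)).

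- n = 9: 1.58 / (1.12 × sqrt(2/9)) = 2.99 on 16 df, power 80.2%. The 80%-power multiple is 1.407 SD, and 1.407 × 1.12 = 1.58.
- n = 6: 1.08 / (0.6 × sqrt(2/6)) = 3.12 on 10 df, power 80.2%. The multiple is 1.796 SD, and 1.796 × 0.6 = 1.08.

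The rows match a t-test on the level SD.

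**Step 2. Put in the SD of the change.** SD(change) = SD × sqrt(2(1 - rho)). This equals the level SD when 2(1 - rho) = 1, that is, at rho = 0.5.

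| rho | factor | power at 1.58, n = 9 | power at 1.08, n = 6 | 80%-power difference, n = 9 | 80%-power difference, n = 6 |
|---|---|---|---|---|---|
| 0.2 | 1.265 | 60% | 60% | 1.99 | 1.36 |
| 0.3 | 1.183 | 66% | 66% | 1.86 | 1.27 |
| 0.4 | 1.095 | 73% | 73% | 1.73 | 1.18 |
| 0.5 | 1.000 | 80% | 80% | 1.58 | 1.08 |
| 0.6 | 0.894 | 88% | 88% | 1.41 | 0.96 |
| 0.7 | 0.775 | 95% | 95% | 1.22 | 0.83 |

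Example, n = 9 and rho 0.2: 1.407 × 1.12 × 1.265 = 1.99.

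**Step 3. Unequal SDs.** If the Day 28 SD is k times the baseline SD, SD(change) = SD × sqrt(1 + k² - 2·rho·k), and the break-even is rho = k/2: 0.375 for k = 0.75, 0.625 for k = 1.25.

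**Step 4. C4.** C4 is adjusted for its own baseline, so its residual SD is SD × sqrt(1 - rho²), which never exceeds the level SD. At the stated C4 differences, power is 80% at rho 0 and 90% at rho 0.5 in both tables, before degrees of freedom are spent on covariates. With three spent, it is 79% (n = 9) and 76% (n = 6) at rho 0, and 89% and 87% at rho 0.5.

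**Step 5. Baseline BSFS as a covariate.** The same residual formula then applies to stool form. With four covariates (df 12 at n = 9, df 6 at n = 6) and the other three assumed to explain nothing, power at 1.58 and 1.08 is 78% and 74% at rho 0, and 89% and 85% at rho 0.5.

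**The case against.** Four objections carry weight.

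- **The tabulated rows are not the planned test.** Section 7.2 describes one ANCOVA, with no separate test in each sequestrant group. A reader might carry the 60% to 95% range over to the whole trial at 15 per group. The documents do not support that, because they state no stool-form difference for that size. If Table 1's 1.58 and SD 1.12 are borrowed, 15 per group gives 84% power at rho 0.2 and 96% at rho 0.5. This stands, and it limits the point to the table rows.
- **The 0.5 threshold needs equal SDs.** This stands. The level SDs in section 7.1 differ by treatment state (1.12 and 0.6). Purely as an illustration, k = 0.6/1.12 = 0.54 puts the break-even at rho of about 0.27.
- **The target effect is the same.** Under randomisation the expected group difference in change equals that in the Day 28 level; only the variance differs. The average daily score at Day 28 is itself a secondary endpoint, to which a level SD applies. This stands, but the power claim is made for the primary endpoint, whose variance is that of the change.
- **The analysis is not biased.** A reader might infer that a null stool-form result could not be interpreted. That goes too far: the confidence interval uses the observed variance, whatever SD was used in planning.

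It would also be tempting to fault both primary endpoints. Step 4 shows no material shortfall for C4. Finally, the phrase about typical baseline results introduces Table 2 only. For Table 1, the evidence that the SD is a level is the mean of 4.4 on the 1-7 scale and the percentage of the baseline mean.

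**Conclusion.** The point holds for the stool-form rows of Tables 1 and 2. Their 80% was computed with the SD of a level, whereas the planned analysis is of a change not adjusted for baseline BSFS. With equal SDs at the two times, power at the stated differences is at least 80% only if rho is about 0.5 or higher. Over the assumed range of 0.2 to 0.7 it runs from 60% to 95%, and the 80%-power difference at 9 per group runs from 1.99 to 1.22 points against the stated 1.58.

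The direction of the error is unknown, because the documents give neither rho nor an SD of the change. The figures in the Step 2 table also take no account of the three planned covariates. If those explain nothing, power at rho 0.5 falls to about 79% (n = 9) and 76% (n = 6). This is a correctable gap in a stated power figure, not a flaw in the estimate or its interval.

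**What to change.** Restate the stool-form rows of section 7.1, and the synopsis power sentence as it concerns stool consistency. Use the SD of the 4-week BSFS change if the investigators can obtain it; the documents do not show that it is available. Otherwise give the detectable difference over a range of rho, with the equal-SD assumption stated, in place of the flat figure of about 80%. In either case, say which kind of SD was used.

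Alternatively, add baseline BSFS, which the pre-treatment diary already collects, as a covariate for the stool-form endpoint. With equal SDs the level SD is then an upper bound. Under the assumptions of Step 5, power is about 78% or more at 9 per group and 74% or more at 6 per group for any rho from 0 upward.

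The cost is a text change, one degree of freedom if the covariate is added, and possibly a less favourable stated figure. No patient, visit or procedure changes.
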